We will use two methodologies to gather data. We will conduct a prospective observational study of children 0-17 years old who present to the ED for care following known or suspected exposure to blunt trauma regardless of whether or not injuries were sustained. Children will be included if they meet any one of the following: (a) undergoing trauma team evaluation, (b) transported from the scene to site facility by EMS, (c)

[figure not shown]

Figure 3: Study Population

undergoing cervical spine imaging at site facility, or (d) transferred to site facility with cervical spine imaging. We will exclude children if they are exposed to a solely penetrating trauma mechanism. Figures 3 and 4 on page 24 represent the study population and study workflow.

CSI, the outcome of interest, is defined as vertebral fracture, ligamentous injury, intraspinal hemorrhage, or spinal cord injury (on either MRI or spinal cord injury without radiographic association) involving the cervical region of the spine (occiput to the 7th cervical vertebra including ligamentous structures attaching the 7th vertebra to the 1st thoracic vertebra). Presence of CSI will be determined by review of study site cervical spine imaging reports and if applicable spine surgeon consultation notes and phone follow-up. At 21 days after the ED visit for injury, the study site medical records will be reviewed for cervical spine imaging and spine surgeon consultation. Children will be considered to have CSI if after cervical spine imaging and if applicable consultation with a spine surgeon; they are determined to have CSI. If imaging report diagnoses conflict with spine surgeon consultation, the treating spine surgeon will be contacted for clarification.

To ensure that there are not missed CSI for those children not undergoing cervical spine imaging, we will review the medical record for follow-up encounters and if necessary, conduct phone follow-up 21-28 days post study enrollment. We will also collect data on patients that are eligible for the study but are not enrolled (missed eligibles).

We estimate that it will require a total observation of at least 22,000 children who are evaluated after blunt trauma to adequately assess our study aims. Enrollment will incorporate a staggered site enrollment plan to allow for an iterative process for the study tool design to meet the study specific aims and objectives. Study objectives include:

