5. For children that did not get imaging: Prior to the patient leaving the ED, the RC provides the family with the Consent, Parental permission, and Authorization cover letter. *Sites will have the option to send this via mail if the RC cannot make contact before the subject leaves the ED.* The RC then completes the Demographics and Disposition Form and the RC continues to step 6.

6. On days 21-28 post ED enrollment, the RC reviews the patient's medical record and completes the Patient Outcome Form. The RC also reviews the chart for cervical spinal imaging and completes the appropriate form.
 - (a) If cervical spine imaging is NOT documented in the record: The RC conducts a phone interview and completes the Phone Follow-Up Form.
 - (b) If cervical spine imaging is documented in the record: The RC and the PI complete the Imaging/Consultation/Surgery Form.
7. For subjects who had abnormal cervical spine imaging, the study adjudicator completes the Patient Diagnosis Form.

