6.5 Diversity Supplement - Overall Study Design

The proposed research will investigate how social factors are associated with pediatric cervical spine injury (CSI) risk, post-injury care and functional outcomes. Our project will use two methodologies to gather data: (1) retrospective review of the electronic medical record and structured medical billing data prepared for the Pediatric Health Information System (PHIS) and (2) fixed-response telephone-administered questionnaire. The final products of this work will lay the groundwork for future studies to create targeted interventions for injury prevention and health care facilitation to improve functional outcomes for at-risk youth.

Children will be included if they were enrolled in the parent grant and sustained a CSI as confirmed by the study neurosurgeon. From the parent study, we will be able to obtain information about the type of CSI diagnosis and acute care interventions as related to the CSI. Our study will conduct an extended chart review for pediatric CSI patients to richly describe social factors present in CSI patients, to further ascertain acute care intervention information and resources at the time of discharge. Additionally, we will also request PHIS IDs to review medical billing data for the incident visit and any subsequent visit within 30 days of the incident visit. PHIS includes patients from over 45 children's hospitals, to which all study sites in the parent grant participates. We will compare CSI patients with the overall population of children in the United States (US) by utilizing census data. Census tract data will be obtained from the American Community Survey. We will retrieve the home zip code at the time of injury for each patient and link in several secondary data sources to capture the social and physical characteristics of the neighborhood/community environment.

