8.1 Specific Aim Analyses

Specific Aim 1. Develop the Pediatric CSI Risk Assessment Tool in children with blunt trauma using prospective observational data obtained from ED providers.

The first step in tool development is the refinement of the original PECARN model into a decision rule that has very high sensitivity for identifying CSI in children with blunt trauma and sufficient specificity to result in a meaningful reduction in the use of spinal precautions and radiographic imaging. To evaluate Aim 1 we will use the prospective observational data obtained from ED providers to refine a clinical decision support tool that has near perfect sensitivity (lower 95% confidence limit $>95\%$) and adequate specificity to reduce unnecessary interventions (lower 95% confidence limit $>40\%$) when screening children for CSIs. To develop the decision rule, we will use binary recursive partitioning on a study population consisting of approximately 13,333 subjects collected from eight PECARN sites.

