We will use multiple analytic techniques to refine the decision rule that will serve as the basis for the Pediatric CSI Risk Assessment Tool. We will use both CART 7.0.0 (San Diego, CA) to perform recursive partitioning for the purpose of building a clinical decision tree and multivariable logistic regression modeling using SAS 9.4 (Cary, NC) to develop a risk model. This is important because each method will result in a tool that has different characteristics. As an example, we will use regression analysis if we determine that the optimal tool is a “risk calculator” in which a child's risk for CSI is calculated based on the child's individual constellation of findings and guidance for CSI evaluation (e.g. nothing versus plain radiographs versus CT) is set for various risk thresholds. We can use regression analysis, as was performed in our pilot work, to determine a set of variables that has sufficient performance characteristics for use as a simple tool in which the presence of any one finding would identify the child as at non-negligible risk for CSI and therefore requiring further evaluation.^{90, 94, 95} Recursive partitioning results in a clinical decision tree in which the resultant tool is a patient care algorithm, with each terminus resulting in a risk estimate on which we base clinical decisions regarding CSI evaluation.^{96, 97} Our ACTA will help determine which type of tool and therefore which analytic techniques for decision rule refinement will be most useful for tool design. It may be that ultimate implementation requires multiple different tools based on various patient scenarios which differ by parameters such as setting, provider type, point of entry into the health care system, and timing within the patient's clinical course.

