Using the results of our ACTA, we will develop conceptual prototypes of the Pediatric CSI Risk Assessment Tool suitable for user testing. We will perform a series of iterative formative usability tests to evaluate the tool prototypes.¹¹⁸⁻¹²⁰ Prototype assessment will be scenario-based and designed to address the various clinical roles and workflows. At each iterative testing period, we will assess the prototypes in terms of usability, utility and effectiveness, but also in supporting the desired outcome of the decision rule. We will modify the prototypes, or if necessary redesign and retest to address the results. With each iteration, the prototypes will increase in the level of detail and functionality they represent. The development and user testing of conceptual system prototypes is well-established in general usability science and moreover in the development of health information technology solutions.^{103, 104, 118, 121, 122} Team members have experience using dedicated software, such as Axure (Axure Software Solutions, San Diego, CA) to support rapid, interactive prototyping of clinical decision support systems suitable for user testing.¹²³⁻¹²⁶

We will include all children that present to the study site EDs, regardless of point of entry into the health care system. While this is important in terms of building a tool that is representative of the full spectrum of children with CSI, this has the potential for resulting in ascertainment bias on the part of the ED providers responding to the assessment forms. In order to address this potential bias, we will determine the operating characteristics of our prediction tool for the entire cohort as well as key sub-samples of children, including those without cervical spine imaging prior to presentation at the study site, those who do not have a trauma team activation, those who arrive via scene response EMS, and those who arrive via private motor vehicle. For any subgroup with poor performance, we will conduct an exploratory analysis by deriving separate rules. As a standard quality measure for observational studies such as this, we will compare the demographic characteristics of enrolled children to those that were eligible and not enrolled.

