In addition, when conducting our analyses, we will examine the operating characteristics of the prediction rule for several high-risk groups including young children (<8 years), children with injuries that require either surgical stabilization or stabilization with an orthotic device for >30 days, children with medical conditions that predispose to CSIs and children who are victims of abusive trauma. For any high-risk group with poor performance, we will conduct an exploratory analysis by deriving separate rules.

While every effort will be made to ensure data quality, we will conduct several analyses to assess the effect of the quality of the data. CART automatically selects surrogate variables in the event that a splitting variable has a missing or unknown value. For regression modeling, we will use multiple imputations to allow for inclusion of records where the provider failed to assess the patient for the clinical finding. Further, if a risk factor in the tool has low prevalence or poor kappa for EMS-ED and ED-Surgical

provider paired observations(lower 95% confidence interval <0.4), the analyses will be re-run excluding the variables for comparison.

Specific Aim 2. Validate the Pediatric CSI Risk Assessment Tool in a separate population of children with blunt trauma using prospective observational data obtained from ED providers.

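### Does section 8.1 promise measures and a separate rule that cannot be produced for children whose injuries need stabilisation?

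*Protocol*

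**What the plan says.** Under Specific Aim 1, Protocol section 8.1 examines the rule's operating characteristics in four high-risk groups. Three are defined by the child: age under 8 years, a predisposing medical condition, and abusive trauma. The fourth is defined by what an injury went on to require: "children with injuries that require either surgical stabilization or stabilization with an orthotic device for >30 days". The kind of injury is not named. A general fallback follows: "For any high-risk group with poor performance, we will conduct an exploratory analysis by deriving separate rules".

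Just before this, the section lists sub-samples by route into care and prior imaging, as a check on ascertainment bias, and gives them a near-identical fallback: "For any subgroup with poor performance, we will conduct an exploratory analysis by deriving separate rules".

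Aim 1 sets a target for sensitivity (lower 95% limit above 95%) "and adequate specificity to reduce unnecessary interventions" (lower 95% limit above 40%). The derivation methods are CART "to perform recursive partitioning for the purpose of building a clinical decision tree and multivariable logistic regression modeling using SAS 9.4". Section 3 fixes the outcome: "CSI, the outcome of interest, is defined as vertebral fracture, ligamentous injury, intraspinal hemorrhage, or spinal cord injury", in the cervical region.

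**The concern.** The fourth group sits in a list of ordinary subgroups but may not be one. In a section about a CSI rule, it is natural to take the injuries as CSIs. The group is then a severity subset of the outcome and contains no child without CSI. Sensitivity can be estimated in it. Specificity and both likelihood ratios cannot, and the predictive values are fixed by construction at 100% (positive) and 0% (negative). Recursive partitioning and logistic regression both need children with and without the outcome, so a CSI rule could not be fitted on members alone.

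Membership also depends on later surgery or on more than 30 days in an orthosis. It is unknown when the child is screened, so a rule reserved for members would have no use at the bedside. Taken at face value, the protocol commits itself to an analysis that cannot be run for one of its four groups.

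**Working it through.** **Inputs.** From the Abstract: development cohort 13,333 children with 240 CSI; validation cohort 8,889 with 160 CSI. From section 2.2: pilot incidence 1.8% (74 of 4,091). The share of CSI that needs stabilisation is not given, so 10% to 75% is assumed.

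**The plan's own figures.** 13,333 × 0.018 = 240.0 and 8,889 × 0.018 = 160.0. Both reproduce.

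**Group content if the injuries are CSIs.** The cohorts hold 13,333 − 240 = 13,093 and 8,889 − 160 = 8,729 children without CSI. None of them is in the group, so true negatives and false positives are both 0 and specificity is 0/0.

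**What sensitivity in the group could show.** With n cases and none missed, the exact two-sided 95% lower limit is 0.025^(1/n).

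| Assumed share of CSI | Development n | Lower limit | Validation n | Lower limit |
|---|---|---|---|---|
| 10% | 24 | 85.8% | 16 | 79.4% |
| 25% | 60 | 94.0% | 40 | 91.2% |
| 50% | 120 | 97.0% | 80 | 95.5% |
| 75% | 180 | 98.0% | 120 | 97.0% |

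These limits describe the precision of the one measure that works. They do not measure a fault.

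**Fitting on members alone.** With every outcome equal to 1, Gini impurity at the root is 0 and no split can improve it. A logistic fit on 120 simulated records of this kind has no finite maximum: the intercept is 6.6 after 5 iterations, 11.6 after 10 and 21.6 after 20. The failure is visible at once and produces no misleading rule.

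**Fitting in the full cohort.** If serious CSI is the outcome among all 13,333 development children, there are 24 to 180 events against 13,309 to 13,153 others. Both classes are present and both methods run. The others include 240 − 24 = 216 down to 240 − 180 = 60 children with CSI that did not need stabilisation, which an analyst would bear in mind when reading the result.

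**How firmly the text ties the injuries to CSI.** Two places could be cited.

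- Section 4.2, step 6(b): "If cervical spine imaging is documented in the record: The RC and the PI complete the Imaging/Consultation/Surgery Form". This is triggered by imaging, not by injury. In the pilot, record review found imaging in 3,201 of 4,091 children (Table 2, 78.2%), against 74 with CSI. At least 3,201 − 74 = 3,127 imaged children had no CSI, so a form completed on that trigger covers mostly children without the outcome.
- Section 6.5 says the parent study lets the supplement "obtain information about the type of CSI diagnosis and acute care interventions as related to the CSI". All supplement subjects have CSI by eligibility (section 6.3), so this wording says little about what section 8.1 means.

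The CSI reading is plausible from context but not fixed by the text.

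**How firmly the text requires fitting on members alone.** It does not say so. The idea comes from the parallel sentence on sub-samples, which concerns a different list with a different purpose. Section 8.1 also allows for several tools suited to different patient scenarios.

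**The case for a change.** The strongest case for a change is that the fallback covers any high-risk group without exception, and that one of the four cannot meet it on the most natural reading. Nearly the same sentence, used a paragraph earlier for sub-samples containing children with and without CSI, plainly means a rule for that sub-sample. A rule for serious CSI in the full cohort changes the outcome, and the section does not describe one. On this view the protocol states something unworkable, and does not merely leave a detail open. One or two sentences would repair it.

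Part of this stands. If the injuries are CSIs, sensitivity is the only informative measure, and a rule fitted on members alone is impossible. On either reading, a rule restricted to members could not be used at screening. But these facts favour the workable reading over the unworkable one: check the rule against serious CSI and, if it does badly, look for a rule that catches serious CSI. The section speaks of operating characteristics in general and does not require specificity for each of these groups. Which measures are reported by group, and how a conditional exploratory re-derivation is set up, are commonly settled in the statistical analysis plan.

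**Conclusion.** No change follows. The conclusion about the group is correct by definition, but it depends on two assumptions the protocol does not make: that the injuries are CSIs, and that any separate rule is fitted on members alone. If the first fails, the group can contain children without CSI. If the second fails, the rule can be fitted against 13,153 to 13,309 other development children, on the assumed 10% to 75% share.

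If both hold, the result is a blank specificity cell and an exploratory tree that does not grow. Neither is a wrong number or a wrong conclusion. The check on sensitivity for serious CSI is a useful safety measure and is fully estimable. The confirmatory targets for sensitivity and specificity in the whole cohorts do not depend on this group. What remains is a loosely worded entry in a conditional, exploratory analysis, which competent analysts would fill sensibly. The assumed share affects only the precision figures, not this conclusion.

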[name] et al. will conduct this work at approximately 18 PECARN trauma centers and collect prospective observational data from EMS and ED providers regarding CSI risk factors for children who undergo emergency evaluation after blunt trauma and follow enrolled subjects for 28 days to determine CSI status. The study will occur in two phases: development (13,333 children; 240 children with CSI) and validation (8,889 children; 160 children with CSI). The study will also capitalize on the research infrastructure to conduct an Applied Cognitive Task Analysis (ACTA) and tool prototype testing that will inform the iterative tool design to ensure that the tool is useable by EMS and ED providers. With data from the development cohort, a useable clinical decision support tool will be constructed that achieves > 95% sensitivity, as well as adequate specificity (> 40%) in the prediction of CSI. Subsequently, [name] et al. will determine the performance characteristics of the tool in the independent validation cohort and in a cohort that has EMS provider observations. The ultimate output from this project will be a set of specifications for the Pediatric CSI Risk Assessment Tool that will include a validated clinical decision rule, validated tool designs and functions, and recommendations for implementation. An accurate, validated, and ultimately field-tested Pediatric CSI Risk Assessment Tool will safely limit unnecessary spinal precautions and radiographic testing for millions of children while helping identify those children who are truly at risk for CSI.

1 Study Summary

Cervical spine injuries (CSI) are serious, but rare events in children.^{1, 2} Spinal precautions (rigid cervical collar and immobilization on a longboard) in the prehospital setting

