however we provided parents/guardians a study information sheet with instructions for withdrawal from further phone follow-up.^{92, 96-99} For children who had cervical spine imaging, we determined presence of CSI by review of the imaging reports by the Site PI with verification of the CSI through review of the spine surgeon's consultation notes. For those children who did not undergo cervical spine imaging in the ED, we made telephone follow-up calls 21-28 days after the ED visit to confirm that the child was free of CSI. To determine whether or not our cohort was representative of all children meeting inclusion criteria, we reviewed daily ED census reports to identify missed eligible children and gathered a limited data set.

Preliminary results from this pilot study support the feasibility of conducting a larger investigation using these established methods. We enrolled 4091 children over 18 months; 84.9% of eligible subjects during enrollment hours and 70.9% of all eligible subjects.⁹² The characteristics of those children that we enrolled were comparable to those that were missed.⁹² We captured the EMS provider's observations 60.2% of the time for those that arrived as a scene response. Importantly, there were 74 children within the cohort ultimately diagnosed with CSI (1.1 injuries per site per month; CSI incidence of 1.8%).⁹²

Table 1 on the next page demonstrates the prospective performance of our retrospectively-identified risk factors in identifying all children with CSI.^{94, 95} For each candidate risk factor, we calculated bivariable relative risks. We explored the PECARN model for CSI as a predictor set and considered children with at least one positive risk factor test positive for CSI risk. The PECARN model risk factors were 90.5% sensitive and 45.6% specific for CSI in the cohort. Retrospective medical record review of the 7 children missed by the PECARN model revealed that all either had a PECARN model risk factor that was not captured in the observational data (n=6; altered mental status and complaint of neck pain) and/or had one of the other observed candidate risk factors (n=5; axial load biomechanics, loss of consciousness, other signs of substantial head injury- skull fracture, upper thoracic tenderness and pain). These findings confirm our previously-identified risk factors for CSI in children.

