To validate the Pediatric CSI Risk Assessment Tool, we hypothesized that the Pediatric CSI Risk Assessment Tool will retain adequate sensitivity (lower 95% confidence limit $>95\%$) and specificity (lower 95% confidence limit $>40\%$) in an independent sample of children presenting for to the ED evaluation following blunt trauma. To evaluate this aim, we will enroll patients from PECARN sites not involved in enrollment for Specific Aim 1. Using a population of 8,889 collected from the prime site and an additional seven different PECARN sites and the prime, we will report standard performance measures to describe the accuracy of the rule: sensitivity, specificity, positive predictive value, negative predictive value, and positive and negative likelihood ratios. We will also report 95% CIs for all above measures. In addition to evaluating the validity of the decision rule, we will continue to perform and report formative testing on the Pediatric CSI Risk Assessment Tool prototypes. If performance of the rule or provider acceptance is low at our interim analysis, we will return to the training set in Aim 1 and approach refining the decision rule using a different process and revalidate. We will report the demographic characteristics of the validation study cohort using means and medians as appropriate for continuous measures and frequencies and percentages for categorical measures.

Specific Aim 3. Validate the Pediatric CSI Risk Assessment Tool in a population of children with blunt trauma using prospective observational data obtained from EMS providers.

Using a set of patients who have data from both EMS and ED providers collected throughout the both the derivation and validation phases of the study we will evaluate the performance of the rule using EMS variables. Additionally, we will assess agreement between EMS and ED providers using the kappa statistics. It is expected that there will be a minimum of 7,444 subjects with data from both EMS and ED providers available for this aim. As in Aims 1 and 2 we will report the decision rules performance based on standard measures: sensitivity, specificity, positive predictive value, negative predictive value, and positive and negative likelihood ratios. We will also report 95% CIs for all above measures. If performance of the rule derived in Aim 1 is poor we will derive an EMS specific rule using similar methods described above.

9 Study Training

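### Does using one sensitivity mark for 240 development and 160 validation injuries set up a sound rule to fail Aim 2?

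*Protocol*

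**What the plan says.** Protocol section 8.1, Specific Aim 1, seeks "a clinical decision support tool that has near perfect sensitivity (lower 95% confidence limit" above 95%). Specific Aim 2 in the same section hypothesizes that, in an independent sample, the tool "will retain adequate sensitivity (lower 95% confidence limit" above 95%). Both aims also ask for a lower limit above 40% for specificity.

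The Abstract gives the planned sizes: "development (13,333 children; 240 children with CSI) and validation (8,889 children; 160 children with CSI"). Section 3 states that "it will require a total observation of at least 22,000 children who are evaluated after blunt trauma to adequately assess our study aims". The protocol gives no assumed true sensitivity and no chance of meeting the mark. It promises 95% confidence intervals for all performance measures without naming a method.

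Aim 2 also has a fallback: "If performance of the rule or provider acceptance is low at our interim analysis, we will return to the training set in Aim 1", refine the rule by a different process and validate again.

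**The concern.** A lower confidence limit depends on the number of events as well as on the estimate. If one limit is required of 240 events and then of 160, the second test is harder. A rule that just meets the mark in development, and performs identically at new sites, could miss it in validation because there are a third fewer events. That result could be misread as a loss of performance, and might prompt refinement of a rule that had not deteriorated.

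The pilot in section 2.2 adds to the unease. There, "there were 74 children within the cohort ultimately diagnosed with CSI", and the existing model detected 67 of them (90.5%). Of the 7 missed, some "had one of the other observed candidate risk factors (n=5"). Adding every such factor would give 72/74 = 97.3%, if observed means recorded on the provider form. That is short of the roughly 99% at which the validation mark becomes comfortable under an exact interval.

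Revalidation after an interim look could be harder still. Under an exact interval, fewer than 72 unused CSI cannot meet the mark even with no miss.

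**Working it through.** **Inputs.** CSI incidence 1.8% (section 2.2); 13,333 and 8,889 children (Abstract); lower 95% limit of sensitivity above 95% in both aims (section 8.1). The interval method is an assumption, so several are shown.

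**The protocol's own counts.** 0.018 × 13,333 = 240.0 and 0.018 × 8,889 = 160.0. Both agree with the Abstract.

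**Misses allowed.** For n CSI and m misses, the two-sided exact (Clopper-Pearson) lower limit is the 2.5% quantile of Beta(n − m, m + 1). The Wald limit is p − 1.96 √(p(1 − p)/n), with p = (n − m)/n.

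| Method | Most misses in 240 (limit) | Next miss | Most misses in 160 (limit) | Next miss |
|---|---|---|---|---|
| Exact | 5 (95.21%) | 94.64% | 2 (95.56%) | 94.62% |
| Wilson | 5 (95.22%) | 94.65% | 2 (95.56%) | 94.63% |
| Jeffreys | 5 (95.49%) | 94.92% | 3 (95.08%) | 94.17% |
| Wald | 6 (95.52%) | 94.95% | 4 (95.08%) | 94.18% |

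**Chance of meeting the Aim 2 mark with unchanged performance.** If the true miss rate is d/240, the chance is the binomial probability of no more than the allowed misses in 160. For d = 5, the expected number of misses is 160 × 5/240 = 3.33.

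| d | Exact or Wilson (2 allowed) | Jeffreys (3 allowed) | Wald (4 allowed) |
|---|---|---|---|
| 1 | 97% | 99.5% | 99.9% |
| 2 | 85% | 95% | 99% |
| 3 | 68% | 86% | 95% |
| 4 | 50% | 72% | 87% |
| 5 | 35% | 57% | 76% |
| 6 | not admitted by Aim 1 | not admitted by Aim 1 | 63% |

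The worst rule that Aim 1 admits therefore passes Aim 2 35% (exact, Wilson), 57% (Jeffreys) or 63% (Wald) of the time. At true sensitivities of 98, 98.5, 99 and 99.5%, the exact figures are 38, 57, 78 and 95%.

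**Which interval the protocol shows.** Table 1 prints 90.5% (83.9-97.2) for ED providers. Wald on 67/74 gives 0.9054 ± 1.96 √(0.9054 × 0.0946/74) = 83.9% to 97.2%, as printed. The EMS column has an upper limit of 103.7%, which only a symmetric interval can produce. The protocol's only printed sensitivity intervals are therefore Wald. Under Wald the two marks coincide, since 6/240 = 4/160 = 2.5%, and 3.33 expected misses lie below the 4 allowed.

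**Would another arrangement do better?**

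- *Stricter Aim 1 mark, at most 2 of 240 missed.* The binomial chance of 3 or more misses in 240 is 43% at a true sensitivity of 99% and 70% at 98.5%. The present mark (6 or more misses, exact) rejects the same rules 3% and 15% of the time.
- *Reversed split, 160 CSI for development and 240 for validation.* The exact chances in validation rise to 65, 85 and 97% at 98, 98.5 and 99%. Development loses 80 of its 240 CSI, and its own mark then allows only 2 misses.
- *Revalidation in 160 new CSI.* This needs 160/0.018, or about 8,889, further children.

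**The case for a change.** The strongest case for a change is that these quantities are fixed in the protocol: the mark, the two event counts and the claim that the total is adequate. The Wald interval behaves badly near 100%, as the printed 103.7% shows, so a careful analyst may well choose an exact or Wilson interval. Then even a rule with 99% true sensitivity meets the Aim 2 mark only 78% of the time. Treating the development estimate as uncertain lowers the chances for 0 to 4 misses of 240 to 98, 88, 75, 61 and 48% (36% for 5), and optimism from fitting would lower them further.

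This much stands: the arithmetic is right for those intervals, and a stated assumed sensitivity would make the plan more informative.

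The practical consequences do not stand. The Aim 2 text does not define low performance at the interim by this confidence limit, and the 65% failure rate is computed at the full 160 CSI. No passage prescribes a not-validated label. Sensitivity, specificity, predictive values and likelihood ratios are all to be reported with intervals, so a reader can tell imprecision from deterioration. The protocol gives no interim timing, so any count of unused CSI is hypothetical, and Aim 2 already asks for an independent sample.

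The pilot is weak evidence against 99%. The exact interval for 72/74 is 90.6% to 99.7%. The "Retrospective medical record review of the 7 children missed by the PECARN model" also found that 6 of them had a model factor that the observational data had not captured.

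**Conclusion.** No change is needed. A common limit on 240 and 160 events does make Aim 2 the harder test under an exact or Wilson interval: a rule at the edge of Aim 1 passes 35% of the time, with the 5/240 miss rate taken as the truth and 160 CSI realized. That figure depends on an unnamed method and a boundary case. The same rule passes 57% of the time under Jeffreys and 76% under Wald. Rules missing 0 to 2 of 240 pass at least 85% of the time under every method tabulated.

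The plan contains no miscalculated figure and misses no stated power. Requiring the same clinical floor in both cohorts is a fair choice, because the floor concerns missed injuries and has no reason to relax with fewer events. Each alternative trades one risk for another: rejecting good rules at Aim 1, weaker development, or more enrolment. Naming the interval method and an assumed sensitivity would add useful detail, but that commonly belongs in a statistical analysis plan and would not alter the design.
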